8.5. Pharmacokinetics

Blood samples for PK analyses will be collected from all randomized patients in accordance with the Schedule of Activities ([Appendix 2](#)). Plasma samples will be assayed for baricitinib using a validated liquid chromatography tandem mass spectrometry (LC/MS/MS) method at a laboratory approved by Lilly or its designee.

On the day of Visit 2, after completion of baseline assessments (including baseline laboratory tests as outlined in the Schedule of Activities) and administration of investigational product, a single PK sample will be collected 15 to 30 minutes postdose. It is important that apart from this single PK sample, all other baseline laboratory samples are taken PREdose.

On the day of Visit 4 and Visit 7, a single predose PK sample will be collected for each visit. Patients will be advised not to take their investigational product prior to visiting the clinic. To reduce the number of blood draws, the predose PK sample may be drawn at the same time as other routine labs required at that visit. Patients can subsequently take their investigational product at any time during their visit to the clinic. The patient should be instructed to take a dose of investigational product from the new packages assigned at that visit. If a patient arrives at the clinic on the day of Visit 4 or Visit 7 after having taken the dose, the PK sample should be drawn with other routine labs randomly at any time postdose; the inability to collect predose samples will not be considered a protocol violation.

On the day of Visit 5, one PK sample will be taken between 1 and 3 hours postdose. The visit should be scheduled to accommodate this sampling. Patients will be advised to record the exact time when the dose was taken at home and report it to the site personnel. Alternatively, patients may take their investigational product upon arrival to the clinic for their visit. To reduce the number of blood draws, the postdose PK sample may be drawn at the same time as other routine labs required at that visit. The inability to collect postdose samples at the specified time will not be considered a protocol violation.

A single PK sample also is to be collected, if possible, from patients who discontinue the study early. In the event of an SAE, up to 2 additional blood samples may be taken at the investigator's discretion. If collected, the PK samples should be collected after the reported event, approximately 6 hours apart and within 24 hours of the patient's last dose.

For any PK samples taken, the actual date and time of PK sample collection and the date and time of last 2 doses prior to the PK sample should be recorded. PK samples will be kept in storage at a laboratory facility designated by Lilly or its designee. Only samples from active doses will be assayed (PK samples from patients on placebo will not be assayed). PK samples may also be assayed for additional exploratory analyses. Bioanalytical samples collected to measure investigational product concentration will be retained for a maximum of 1 year following the last patient visit for the study.

8.6. Pharmacodynamics

Plasma, serum, and urine samples will be collected for evaluation of pharmacodynamic (PD) markers, including, but not limited to anti-dsDNA, complement, anti-Sm, anti-RNP, anti-SSA/Ro, and anti-SSB/La.

The markers will not include any markers of the patient's genetic makeup. Samples will be collected at the times noted in the Schedule of Activities.

Bioanalytical samples collected to measure PD markers will be identified by the patient number (coded) and retained for a maximum of 1 year following last patient visit for the study at a facility selected by Lilly or its designee.

8.7. Genetics

8.7.1. Whole Blood Sample for Pharmacogenetic Research

A whole blood sample will be collected for pharmacogenetic analysis as specified in the Schedule of Activities ([Appendix 2](#)) where local regulations allow.

Samples will not be used to conduct unspecified disease or population genetic research either now or in the future. Samples will be used to investigate variable response to baricitinib and to investigate genetic variants thought to play a role in SLE. Assessment of variable response may include evaluation of AEs or differences in efficacy.

All samples will be coded with the patient number. These samples and any data generated can be linked back to the patient only by the investigator site personnel.

Samples will be retained for a maximum of 15 years after the last patient visit for the study, or for a shorter period if local regulations and/or ethical review boards (ERBs)/investigational review boards (IRBs) impose shorter time limits, at a facility selected by Lilly or its designee. This retention period enables use of new technologies, response to regulatory questions, and investigation of variable response that may not be observed until later in the development of baricitinib or after baricitinib become(s) commercially available.

Molecular technologies are expected to improve during the 15-year storage period and therefore cannot be specifically named. However, existing approaches include whole genome or exome sequencing, genome wide association studies, and candidate gene studies. Regardless of technology utilized genotyping data generated will be used only for the specific research scope described in this section.

8.8. Biomarkers

Biomarker research is performed to address questions of relevance to drug disposition, target engagement, PD, mechanism of action, variability of patient response (including safety), and clinical outcome. Sample collection is incorporated into clinical studies to enable examination of these questions through measurement of biomolecules including ribonucleic acid (RNA), proteins, lipids, and other cellular elements.

Serum, plasma, urine, and whole blood RNA samples for non-pharmacogenetic biomarker research will be collected at the times specified in the Schedule of Activities ([Appendix 2](#)) where local regulations allow.

Samples will be used for research on the drug target, disease process, variable response to baricitinib, pathways associated with SLE, IFN signature, mechanism of action of baricitinib, and/or research method or in validating diagnostic tools or assay(s) related to SLE.

All samples will be coded with the patient number. These samples and any data generated can be linked back to the patient only by the investigator site personnel.

Samples will be retained for a maximum 15 years after the last patient visit for the study, or for a shorter period if local regulations and ERBs impose shorter time limits, at a facility selected by

Lilly or its designee. This retention period enables use of new technologies, response to regulatory questions, and investigation of variable response that may not be observed until later in the development of baricitinib or after baricitinib becomes commercially available.

8.9. Health Outcomes

The self-reported questionnaires will be administered prior to any clinical assessments according to the Schedule of Activities ([Appendix 2](#)) in countries where the questionnaires have been translated into the native language of the region and linguistically validated. These instruments will be captured at the site via an electronic patient-reported outcomes (ePRO) device.

8.9.1. Patient's Global Assessment of Disease Activity

The Patient's Global Assessment of Disease Activity is a single-item, patient reported scale developed for the assessment of the patient's overall rating of their disease activity due to SLE. The scale measures disease activity through a 5 point Likert scale ranging from 0 ("No disease activity") to 4 ("Severe disease activity") at its worst over the past 7 days (Felson et al. 1993; van Tuyl and Boers 2012).

8.9.2. Brief Pain Inventory (BPI)–Worst Pain Numeric Rating Scale (NRS)

The BPI-sf modified is a 5-item, self-administered questionnaire developed for the rapid assessment of pain, and provides information on the intensity of pain (the sensory dimension) as well as the degree to which pain interferes with function (the reactive dimension). The BPI-sf modified also asks questions about pain relief, pain quality, and the patient's perception of the cause of pain. The worst pain item of the BPI-sf modified is a 1-item, self-administered question developed for the rapid assessment of pain intensity. The worst pain item uses an 11-point scale from 0 ("No pain") to 10 ("Pain as bad as you can imagine") NRS. Since pain can be quite variable over a day, the worst pain item asks patients to rate their pain at its worst over the past 7 days (Cleeland 1991; Cleeland and Ryan 1994).

8.9.3. Brief Pain Inventory (BPI)–Worst Joint Pain NRS

The worst joint pain item is adapted from the worst pain item of the BPI-sf modified. It is a single-item, self-administered question developed for the rapid assessment of pain intensity of the joints. The worst joint pain item uses an 11-point scale from 0 ("No joint pain") to 10 ("Joint pain as bad as you can imagine") NRS. Since pain can be quite variable over a day, the worst joint pain item asks patients to rate their joint pain at its worst over the past 7 days (Cleeland 1991; Cleeland and Ryan 1994).

8.9.4. Brief Fatigue Inventory (BFI)–Worst Fatigue NRS

The BFI is a brief patient-reported questionnaire for the rapid assessment of fatigue severity and the impact of fatigue on daily functioning. The BFI contains 10 items; however, the first item is not included in the overall scoring of the scale as it asks about usual fatigue over the past week with the respondent answering "yes" or "no." The remaining 9 items assess fatigue severity

(3 items) and impact of fatigue on daily functioning (6 items). The worst fatigue item of the BFI is a brief patient-reported question for the rapid assessment of worst fatigue severity. The item features an 11-point numeric scale (0 [“No fatigue”] to 10 [“Fatigue as bad as you can imagine”]) and asks patients to rate their fatigue at its worst over the past 7 days. The BFI is implemented without a user manual. The instructions for the completion are embedded within the questionnaire, and patients will read the instructions before responding to the corresponding item (Mendoza et al. 1999; Wolfe 2004).

8.9.5. Short-Form 36-item Health Survey v2 (SF-36)

The SF-36v2 Acute measure is a subjective, generic, health-related quality of life instrument that is patient-reported and consists of 36 questions covering 8 health domains: physical functioning, bodily pain, role limitations due to physical problems, role limitations due to emotional problems, general health perceptions, mental health, social function, and vitality. Each domain is scored by summing the individual items and transforming the scores into a 0 to 100 scale with higher scores indicating better health related quality of life. In addition, 2 summary scores, the PCS and the MCS, will be evaluated based on the 8 SF-36v2 Acute domains. The acute version of this instrument has a 1 week recall period (Brazier et al. 1992; Ware and Sherbourne 1992).

9. Statistical Considerations and Data Analysis

9.1. Determination of Sample Size

Approximately 300 patients will be randomized in a 1:1:1 ratio to the baricitinib 4-mg, 2-mg, and placebo treatment groups. With 100 patients per treatment group, this study will have approximately 81% power to detect a difference between baricitinib 4-mg or 2-mg and placebo of $\geq 20\%$ in remission rates of rash and/or arthritis at Week 24. The sample size was determined based on the chi-square test with 2-sided type I error of 5% and 40% remission rate of rash and/or arthritis in placebo treatment group. The sample size calculation was performed using nQuery® Advisor 7.0 software.

9.2. General Statistical Considerations

Statistical analysis of this study will be the responsibility of Eli Lilly and Company.

Efficacy analyses will be conducted on the modified intent-to-treat (mITT) population. This set includes all data from all randomized patients receiving at least 1 dose of the investigational product according to the treatment the patients were assigned.

All tests of treatment effects will be conducted at a 2-sided alpha level of 0.05, unless otherwise stated.

Any change to the planned data analysis methods described in the protocol will require an amendment ONLY if it changes a principal feature of the protocol. Any other change to the data analysis methods described in the protocol, and the justification for making the change, will be described in the clinical study report (CSR). Additional exploratory analyses of the data will be conducted as deemed appropriate.

The SAP will provide analysis details.

9.2.1. General Considerations for Analyses

In general, continuous data will be summarized in terms of the mean, standard deviation, minimum, maximum, median, and number of observations. Categorical data will be summarized as frequency counts and percentages.

Comparisons between the baricitinib 4-mg or baricitinib 2-mg and placebo groups will be performed for all analyses for the Double-Blinded Treatment Period. No adjustment for multiplicity will be done for these comparisons.

Treatment comparisons of categorical efficacy variables will be made using a logistic regression analysis with treatment, baseline disease activity (SLEDAI-2K < 10 versus SLEDAI-2K ≥ 10), baseline anti-dsDNA status (positive; negative), and region in the model. The proportions and 95% confidence interval (CI) will be reported. Missing data will be imputed using the NRI method.

Treatment comparisons of continuous efficacy and health outcome variables will be made using mixed-effects models for repeated measures (MMRM) model with treatment, baseline score,

baseline disease activity (SLEDAI-2K <10 versus SLEDAI-2K ≥ 10), baseline anti-dsDNA status (positive; negative), region, visit, and the interaction of treatment-by-visit as fixed factors. An unstructured covariance matrix will be used to model the within-patient variance-covariance errors. Type III sums of squares for the least squares (LS) means will be used for the statistical comparison; the 95% CI will also be reported. Treatment group comparisons with placebo at Week 24 and other visits will be tested.

Fisher exact test will be used for all AE, baseline, discontinuation, and other categorical safety data. Continuous vital signs and laboratory values will be analyzed by an analysis of covariance (ANCOVA) with treatment and baseline values in the model. Other continuous safety variables will be analyzed based on t-tests, or as otherwise stated.

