To evaluate the effect of baricitinib 4-mg QD or 2-mg QD compared to placebo on patient-reported outcomes (PROs) in patients with SLE receiving concomitant standard therapy over 24 weeks.	
 • Change in worst pain item from the Brief Pain Inventory (BPI) at Week 12 and 24 compared to baseline • Change in worst joint pain item from the BPI at Week 12 and 24 compared to baseline • Change in worst fatigue item from the Brief Fatigue Inventory (BFI) at Week 12 and 24 compared to baseline • Change in mental component score (MCS), physical component score (PCS), and domain scores in the Short-Form 36-item health survey version 2 (SF-36v2) acute at Week 12 and 24 compared to baseline.
To explore dose/exposure response relationships with key efficacy (such as SLEDAI-2K) and safety (such as hematologic parameters) endpoints of interest.	
 • The relationship between baricitinib PK and key efficacy and safety endpoints will be characterized using popPK/pharmacodynamics (popPK/PD) modeling.

4. Study Design

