6.7. Treatment Compliance

Patient compliance with investigational product will be assessed at each visit during the treatment period (Visit 3 through Visit 9) by counting returned tablets. Deviations from the prescribed dosage regimen should be recorded in the electronic case report form (eCRF).

A patient will be considered significantly noncompliant if he or she misses more than 20% of the prescribed doses of investigational product (full doses) during the study, unless the patient's investigational product is withheld by the investigator for safety reasons. Similarly, a patient will be considered significantly noncompliant if he or she is judged by the investigator to have intentionally or repeatedly taken 20% more than the prescribed amount of medication.

Patients will be counseled by study staff on the importance of taking the investigational product as prescribed, as appropriate.

Patients' compliance will be further defined in the SAP.

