9.2.3. Baseline Definition

Baseline will be defined as the last available value before the first dose of investigational product for both efficacy and safety analyses. In most cases, this will be the measure recorded at Week 0 (Visit 2). Change from baseline will be calculated as the visit value of interest minus the baseline value. For the post-treatment Follow-up Period, the baseline is defined as the last nonmissing assessment on or prior to entering the post-treatment Follow-up Period, that is, on or prior to the Week 24 visit (Visit 9), or the end of treatment visit (including ETV).

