9.4.2. Secondary Analyses

Treatment comparison between baricitinib dose regimens (4-mg or 2-mg) and placebo for the change from baseline in SLEDAI-2K score at Week 24, and the change from baseline in patient's global assessment of disease activity at Week 24 will be analyzed using MMRM method with treatment, baseline disease activity (SLEDAI-2K <10 versus SLEDAI-2K \geq 10), baseline anti-dsDNA status (positive; negative), region, visit, and the interaction of treatment-by-visit as fixed factors. An unstructured covariance matrix will be used to model the within-patient variance-covariance errors. Type III sums of squares for the LS means will be used for the statistical comparison; the 95% CI will also be reported. Treatment group comparisons with placebo at Week 24 and other visits will be tested.

Treatment comparison between baricitinib dose regimens (4-mg or 2-mg) and placebo for the proportion of patients achieving a SRI-4 response and for the proportion of patients achieving a reduction of \geq 4 points in SLEDAI-2K score at Week 24 will be analyzed using the logistic regression model with treatment, baseline disease activity (SLEDAI-2K <10 versus SLEDAI-2K \geq 10), baseline anti-dsDNA status (positive; negative), and region in the model. The proportions and 95% CI will be reported. Missing data will be imputed using the NRI method.

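### The general MMRM ties one baseline slope across all visits; if that slope changes over time, Week 24 contrasts for repeated continuous endpoints lose some precision

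*Protocol*

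**What the plan says.** Section 9.2.1 describes an "MMRM) model with treatment, baseline score", followed by the SLEDAI-2K stratum, anti-dsDNA status, "region, visit, and the interaction of treatment-by-visit as fixed factors". The synopsis gives the same list. On the covariance, Section 9.2.1 says: "An unstructured covariance matrix will be used to model the within-patient variance-covariance errors". The treatment effect may therefore differ at each visit, but baseline score has a single coefficient.

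The outcome is change from baseline; Section 9.2.3 says: "Change from baseline will be calculated as the visit value of interest minus the baseline value".

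Section 9.4.2 gives a separate model for the two continuous secondary endpoints (SLEDAI-2K score and Patient's Global Assessment): "MMRM method with treatment, baseline disease activity" and the other factors, with no baseline score.

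In the Schedule of Activities (Appendix 2), joint counts, CLASI, Physician's Global, the pain and fatigue items, anti-dsDNA and C3/C4 are measured at seven post-baseline treatment visits (Weeks 2, 4, 8, 12, 16, 20 and 24). SF-36 has two (Weeks 12 and 24), the RNA sample for the interferon signature four (Weeks 2, 4, 12 and 24), and the SLICC/ACR index one (Week 24).

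**The concern.** A baseline value often predicts a measurement two weeks later better than one 24 weeks later. Three features of this design make that plausible. The visits span Weeks 2 to 24. Corticosteroid dose may be reduced, and returned to no more than its baseline level, up to Week 16 (Section 6.8). Patients are also selected for active disease at the baseline visit itself (Section 5.1.2).

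If the slope does fall, a single coefficient is a weighted average of the visit-specific slopes. Under an unstructured covariance the early visits, with the smaller residual variance, pull it towards themselves. Week 24 is then adjusted with a slope that is not its own. Part of the baseline variation that could have been removed stays in the residual, and the contrast is less well protected against chance baseline imbalance. What is at stake is precision at Week 24, the main visit, for the repeated continuous endpoints.

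**Working it through.** **The plan's own figure.** Section 9.1 states about 81% power with 100 patients per arm, on a "2-sided type I error of 5% and 40% remission rate" in the placebo group and a 20-point difference. For the chi-square test, z = (0.20 × √100 − 1.96 × √(2 × 0.5 × 0.5)) / √(0.4 × 0.6 + 0.6 × 0.4) = (2.000 − 1.386) / 0.693 = 0.886, so power is 0.812. The figure reproduces, but it concerns the binary primary endpoint. The protocol states no SD, correlation or power for any MMRM endpoint.

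**Inputs from the protocol.** Seven visits at the weeks above; change from baseline as outcome; unstructured covariance; baseline score as a main effect only.

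**Assumptions.** SD of 1 at every visit and complete data. The baseline-to-visit correlation β(t) falls linearly in time from Week 2 to Week 24. Residual variance is 1 − β(t)². Residual correlation is 0.7 per 4 weeks, varied from 0.6 to 0.9. The slope of change on baseline is β(t) − 1, so differences between visits are the same as for β(t).

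**Formulae.** Randomisation makes baseline independent of treatment. With R the residual covariance matrix and 1 a vector of ones, the tied slope converges to b = (1′R⁻¹β) / (1′R⁻¹1). The Week 24 residual variance is
- with visit-specific slopes: v = 1 − β(24)²
- with a tied slope: v + (β(24) − b)²

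so the inflation is (β(24) − b)² / v.

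**Worked example.** For 0.80 falling to 0.55: v = 1 − 0.3025 = 0.6975; b = 0.7138; (0.5500 − 0.7138)² = 0.0268; 0.0268 / 0.6975 = 3.8%.

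| β, Week 2 to Week 24 | b | v | Week 24 variance increase | Effective n per 100 | Increase at residual correlation 0.6 to 0.9 |
|---|---|---|---|---|---|
| 0.50 to 0.50 | 0.500 | 0.750 | 0% | 100 | 0% |
| 0.75 to 0.60 | 0.688 | 0.640 | 1.2% | 99 | 1.2 to 1.7% |
| 0.80 to 0.55 | 0.714 | 0.698 | 3.8% | 96 | 3.5 to 6.4% |
| 0.85 to 0.50 | 0.756 | 0.750 | 8.8% | 92 | 7.9 to 15.7% |
| 0.85 to 0.45 | 0.749 | 0.798 | 11.2% | 90 | 10.0 to 20.1% |
| 0.90 to 0.40 | 0.820 | 0.840 | 21.0% | 83 | 18.5 to 36.0% |

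**Simulation check of the standard error.** 250 trials per scenario, two arms of 100, maximum-likelihood unstructured MMRM, residual correlation 0.8, decay linear over visit number, complete data:
- 0.70 to 0.40: mean SE 0.1288 by visit and 0.1318 tied, an increase of 2.3% (formula: 2.3%)
- 0.80 to 0.30: 0.1345 and 0.1460, an increase of 8.6% (formula: 8.7%)

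With no true effect, mean Week 24 estimates stayed within 0.015 SD of zero under both models, with and without missing-at-random dropout.

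**The case against.** A main-effect baseline covariate with an unstructured covariance is a valid MMRM, and nothing here is biased. The protocol leaves analysis detail to the SAP (Sections 9.2, 9.4.3 and 9.7.1), which was not available for this review and may already contain the interaction. The loss is also assumed: with a constant slope it is zero.

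Much of this stands. It limits the point to precision, makes it conditional, and keeps it modest. It does not remove it. The protocol lists the fixed effects explicitly, including one interaction by visit, so a literal implementation ties the slope; this is a stated model and not an omitted detail.

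A reader might infer that the trial's main comparisons are weakened. The documents do not support that. The primary endpoint (Section 9.4.1) and the SRI-4 and 4-point SLEDAI-2K responder endpoints (Section 9.4.2) use logistic regression. The two continuous secondary endpoints have no baseline score in their own model, so as written no slope is tied there. Omitting the score is a separate discrepancy and can cost more. In the flat 0.50 case, v + (β(24) − 1)² = 0.75 + 0.25 = 1.00, and √(1.00 / 0.75) = 1.155: a 15.5% larger standard error, before any recovery from the SLEDAI-2K stratum.

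Nor does seven visits hold for every continuous endpoint. SF-36 has two, the interferon signature four, and the SLICC/ACR index one, where a single slope loses nothing.

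**Conclusion.** The point holds as a conditional and inexpensive efficiency improvement. As specified, the general MMRM fits one baseline slope across visits. In large samples this cannot improve Week 24 precision, and it reduces it whenever the Week 24 slope differs from the pooled slope.

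At residual correlation 0.7 the Week 24 variance rises by 0% for a flat slope, about 1 to 4% for mild to moderate decay, and about 9 to 21% only for steep decay such as 0.85 to 0.50 or 0.90 to 0.40. Stronger residual correlation makes the loss larger. All of this rests on assumed correlations and equal SDs, because the protocol gives neither.

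It would go too far to say that the Week 24 comparisons are less precise as a matter of fact, or by how many points of power: the slope pattern is undocumented and the protocol states no effect size for these endpoints. As the text stands, the seven-visit case covers joint counts, CLASI, Physician's Global, the pain and fatigue items, anti-dsDNA and C3/C4, which are all exploratory.

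**What to change.** In Section 9.2.1 and the synopsis, add the baseline score-by-visit interaction to the MMRM fixed effects. In Section 9.4.2, include baseline score and the same interaction, so that the specific and general models agree. If the SAP already contains these terms, bring the protocol wording into line with it.

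The change is one phrase in each place, made before unblinding. It uses 7 − 1 = 6 extra degrees of freedom for a seven-visit endpoint, 3 for the interferon signature and 1 for SF-36, in about 300 patients. There is no large-sample loss at Week 24 if the slope turns out to be constant. No data collection or sample size changes.
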